# 13.0 Risks to Subjects\*

13.1 The study will require an IV contrast injection, which carries a small risk of contrast reaction, which will be minimized by the study personnel by patient pre-screening and following MDACC IV contrast injection protocols.

13.2 The extra imaging study carries small extra dose of ionizing radiation, approximately 30% more than a standard 2D mammogram, but less than a combination mode 3D mammogram.

13.3 CEM may detect abnormalities in the breasts which are not seen with mammography or ultrasound and may require CEM- guided biopsies.

# **14.0** Potential Benefits to Subjects\*

14.1 CEM is known to have higher sensitivity for cancer detection than MG and US and may benefit the study patients by finding BC that were not previously seen on other imaging studies.

14.2 CEM may eliminate the need for breast MRI, which is a costly and time-consuming study that can delay treatment in BC patients.

14.3 The presence of a CEM-guided biopsy device can enable direct biopsy of CEM- only detected lesions without the need for breast MRI or breast MRI-guided biopsies.

## 15.0 Data Management\* and Confidentiality

### 15.1 Statistical considerations

The primary objective of this study is to compare the accuracy of CEM and LE images (FFDM equivalent) for the detection of additional cancer sites in the affected breast and in the contralateral breast among patients with known BC diagnosed or highly suspicious at an outside facility and presenting to MD Anderson for staging imaging. The images of CEM/LE and DBT for each patient will be read/reviewed by 5 radiologists, and the majority agreement among 5 radiologists on the lexicon and BI-RADS assessment will be used for consensus. If all 5 radiologists disagree, then a consensus conference will be held. Pathology results will be considered the ground truth. Breast tissue lesions will be categorized as positive if determined as invasive cancer or DCIS, and otherwise will be categorized as negative that includes the lesions of uncertain malignant potential without subsequent surgical upgrade to invasive cancer or DCIS.

The primary outcome of this study is accuracy determined by comparing the CEM/LE results to that of the pathologic evaluations. Specifically, it is defined as the number of concordant cases between CEM/LE and pathologic evaluation divided by the total sample size. Secondary outcomes include sensitivity, specificity, negative predictive value (NPV) and positive predictive value (PPV). Sensitivity (specificity) is defined as the number of correctly diagnosed positive (negative) cases divided by the total number of confirmed positive (negative) cases, NPV is defined as the number of true negative lesions obtained from CEM/LE divided by the corresponding total predicted number of negative lesions. The PPV is similarly defined for positive breast lesions. Cancer detection rate is defined as number of invasive malignancy or DCIS divided by the total sample size.

A successful CEM guided biopsy is defined as a biopsy which successfully sampled the abnormality in question. This procedure will be considered feasible if 95% patients or more have successful CEM guided biopsy among those who will undergo this procedure, which is similar to the success rate of the prone stereotactic vacuum assisted biopsies [41].

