# 1.0 Study Summary

| Study Title
Study Design
Study Specific
Abbreviations/
Definitions | Added value of contrast enhanced mammography for breast
cancer staging in patients referred for a second opinion to a
tertiary cancer center
Prospective observational cross-sectional or correlational
study
CEM: contrast enhanced mammography
BC: breast cancer
OSF: outside facility (medical institution or office outside of
MD Anderson)
FFDM: full field digital mammogram (2D mammogram)
LE: low energy images (a part of CEM exam, FFDM
equivalent)
DBT: digital breast tomosynthesis (3D mammogram)
US: ultrasound   |
|--|--|
| Primary Objective
Secondary
Objective(s)                                 | 
 
To compare the accuracy of CEM and LE images (equivalent of FFDM as the standard of care) for the detection of additional cancer sites in the affected breast and in the contralateral breast. For the purpose of the study, up to 4 additional biopsy sites will be included in the analysis.
 
1. To evaluate the sensitivity, specificity, positive and negative predictive value of CEM compared to LE CEM images (FFDM equivalent), DBT and ultrasound for the detection of additional malignant lesions in the ipsilateral and contralateral breast.
 
2. To evaluate the difference of the index cancer size estimation among CEM, LE images, DBT, and ultrasound compared to pathology measurements as the ground truth.
 
3. To evaluate the incremental cancer detection rate provided by CEM, DBT, and US compared to the OSF diagnosis.
 
 |
| Exploratory
Objective(s)  | 
 
To evaluate the rate of referral to breast MRI in the study cohort.
 
To evaluate the performance of MRI for breast cancer diagnosis and compare it with other imaging modalities of CEM, LE images, DBT and ultrasound.
 
To evaluate the feasibility of CEM-guided biopsy of CEM- only detected lesions. The technical success of CEM guided biopsies will be determined by the
 
  |

|  | fraction of biopsies that achieve adequate sampling of the target.  |  |  |
|--|---|--|--|
| Research
Intervention(s)/
Investigational
Agent(s)
IND/IDE # | IV injection of iodinated contrast material   |  |  |

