### 1. LE images:

- Laterality
- Clock position
- 3 dimensional measurements of the index mass (antero-posterior, craniocaudal, transverse), when possible
- View demonstrating the finding best (CC, MLO, LM)
- The number, laterality, and clock position of additional lesions
- Breast density (Bi-RADS A-D)
- BI-RADS assessment per lesion using the 7-point BI-RADS® scale (1, 2, 3, 4a, 4b, 4c, 5) (Fig.3). BI-RADS categories 1-3 will be considered negative, and BI-RADS categories 4-5 will be considered positive.

2. DBT images:

- Laterality
- Clock position

- 3 dimensional measurements of the index mass in question (anteroposterior, craniocaudal, transverse), when possible
- View demonstrating the finding best (CC, MLO, LM)
- The number, laterality, and clock position of additional lesions
- BI-RADS assessment using the 7-point BI-RADS® scale (1, 2, 3, 4a, 4b, 4c, 5) (Fig.3). BI-RADS categories 1-3 will be considered negative, and BI-RADS categories 4-5 will be considered positive.

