### 15.2 Sample size

In two recent studies, the authors reported the accuracies of 78.0% (versus 69.0% for MG) [35] and 79.8% (versus 65.3% for MG) [36], respectively. We utilize these clinical evidences for our sample size justifications. Using a two-sided extended McNemar test with a significance level of 0.05, a sample size of 83 patients provides 80% power to detect an accuracy difference of 12% between the two modalities of CEM and FFDM assuming the discordant of 20%. The method proposed by Wu (2018) was used to calculate the sample size, where the multiple lesions were adjusted via the average number of lesions and the variance that were assumed to be 1.4 and 1, respectively [37]. We further assumed the intracluster correlation of 0.4, and 0.2 for the intracluster correlation of the discordant pairs.

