### 15.3 Statistical analysis plan

Descriptive statistics will be used to summarize clinical variables of interest. Specifically, categorical measures will be summarized using frequencies and percentages and continuous measures will be summarized using means, standard deviations, medians, and ranges. Outcome variables of cancer detection rate, accuracy, sensitivity, specificity, PPV, and NPV will be estimated along with 95% confidence intervals; and compared between the modalities using the McNemar test or the weighted generalized score statistic proposed by Kosinski [38], if deemed appropriate . To account for multiple lesions, outcome variables will be analyzed using generalized liner mix models or extended McNemar's test [39-41], and additional analyses may be further performed if deemed appropriate.

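### Section 15.1 does not fit the per-lesion design: accuracy is divided by the sample size (83 patients), the detection rate names no modality, and the reference standard differs between sections

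*Combined protocol and SAP*

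**What the plan says.** **Unit of the primary outcome.** In 15.1, for accuracy, "it is defined as the number of concordant cases between CEM/LE and pathologic evaluation divided by the total sample size". Sections 1.0, 10.1 and 15.2 give the sample size as 83, counted in patients or subjects, and no other total is stated. The remaining text is about lesions:

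- Sections 1.0 and 4.1, on the primary objective and endpoint: "up to 4 additional biopsy sites will be included in the analysis".
- The same paragraph of 15.1: "NPV is defined as the number of true negative lesions obtained from CEM/LE", with PPV defined in the same way.
- Section 15.2: "the multiple lesions were adjusted via the average number of lesions and the variance that were assumed to be 1.4 and 1" respectively. It adds: "We further assumed the intracluster correlation of 0.4, and 0.2 for the intracluster correlation of the discordant pairs".
- Section 15.3: outcomes are "compared between the modalities using the McNemar test" or a weighted score statistic. It then says: "To account for multiple lesions, outcome variables will be analyzed using generalized liner mix models" or the extended McNemar test.
- Section 5.9, for the low-energy (LE) images: "BI-RADS assessment per lesion using the 7-point" scale. The DBT and CEM lists also ask for a BI-RADS assessment but do not say that it is per lesion.

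**Detection rate.** Section 15.1 divides the count of invasive cancers and DCIS by the total sample size. Section 2.2 wants the increment that CEM, DBT and ultrasound each provide over the outside facility's diagnosis, and 15.3 compares the rate between modalities.

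**Reference standard.** Sections 5.6 and 15.1 use pathology, and 5.6 accepts both biopsy and surgical specimens. The Follow-up section after 5.9 lets biopsy, follow-up or both settle true positives and true negatives.

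**The concern.** Three definitions behind the primary and secondary results are either inconsistent or cannot do the job set for them.

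The accuracy formula points to a patient denominator in a design built on lesions. It does not define a case, and no rule reduces several lesions in one woman to a single result.

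The detection-rate formula depends only on how many cancers the cohort has. Every modality therefore receives the same figure, and a comparison between modalities has nothing to compare.

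The reference rule decides whether a site without tissue can count as a true or false result. Accuracy, specificity and NPV therefore depend on which section the analyst follows.

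If these stay open, unit and reference would be settled at analysis, when the results of each choice could be known.

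**Working it through.** **1. Does the plan's own sample size tell us the unit?**

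Inputs, all from 15.2: two-sided alpha 0.05, power 80%, difference d = 0.12, discordance p = 0.20, mean lesions m = 1.4, variance v = 1, correlations 0.4 and 0.2.

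Independent pairs needed:

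(1.96 × √p + 0.8416 × √(p − d²))² / d²
= (1.96 × √0.20 + 0.8416 × √0.1856)² / 0.0144
= (0.8765 + 0.3626)² / 0.0144 = 106.6.

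Clustering, with varying numbers of lesions:

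- Multiplier: m + v/m − 1 = 1.4 + 0.714 − 1 = 1.114.
- Correlation: 0.4 × 0.2 = 0.08. This product is an assumption; the documents do not print how the two values combine.
- Design effect: 1 + 1.114 × 0.08 = 1.089.
- Patients: 106.6 × 1.089 / 1.4 = 82.95, so 83, as stated.
- Check: 83 × 1.4 = 116.2 lesions; 116.2 / 1.089 = 106.7 effective pairs; power 80.0%.

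Range over the assumed combined correlation, rounded up to whole patients: 0 gives 77, 0.08 gives 83, 0.2 gives 94, 0.4 gives 111. The match at 0.08 is not unique: a correlation of 0.2 without the variance term gives 82.25, also 83. Both routes use lesions.

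One pair per patient, with the same d and p:

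(0.12 × √83 − 0.8765) / √0.1856 = (1.0933 − 0.8765) / 0.4308 = 0.503, so power is 69.3%. For 80%, 107 patients would be needed.

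The stated power therefore agrees with a lesion denominator and not with one result per patient.

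**2. What does the 80% depend on?**

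The 116.2 lesions must all be additional lesions, averaged over all 83 patients. Section 15.2 does not say whether 1.4 leaves out the index lesion or counts patients with no additional site as zero. Suppose instead that 1.4 applies only to patients with a site, and a share s has none. The share is an assumption; the documents give none. Effective pairs are 83 × (1 − s) × 1.4 / 1.089:

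| s (assumed) | Lesions | Effective pairs | Power |
|---|---|---|---|
| 0 | 116.2 | 106.7 | 80.0% |
| 10% | 104.6 | 96.0 | 75.6% |
| 25% | 87.2 | 80.0 | 67.6% |
| 40% | 69.7 | 64.0 | 57.7% |

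**3. Detection rate.**

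In the 15.1 formula, numerator and denominator are both properties of the cohort. Neither changes when one moves from CEM to DBT or ultrasound, so the difference between modalities is zero by construction. Nor is anything removed for cancers already in the outside diagnosis, so the result is not the increment asked for in 2.2.

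**4. Reference standard.**

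Take a site that was never sampled and stayed quiet during the 12 months of follow-up. Under 5.6 and 15.1 it has no truth value and does not enter. Under the Follow-up section it can be a true negative, or a false positive if a reader called it suspicious. Accuracy, specificity and NPV then have different denominators under the two rules.

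**The case against.** The best defence is that the unit is clear in context. The endpoint speaks of additional biopsy sites, 15.2 and 15.3 both speak of multiple lesions, and 15.1 also uses cases for sensitivity and specificity, so sample size could be taken loosely to mean lesions. That is probably the intent, and the power check supports it. But the primary formula does not say so, and elsewhere the term only ever means 83 patients.

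Likewise, 2.2 and 4.2 name the modalities for the detection rate. This shows what was intended, but the 15.1 formula does not carry it out.

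The BI-RADS point is thin by itself. The CEM list records number, side and clock position of additional lesions; the assessment after adding CEM can be read as an update of the per-lesion LE assessment; and 5.3 plans correlation per lesion. The primary test is also largely inferable, since 15.2 is powered on the extended McNemar test. Both are details to complete.

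A reader might go further and infer that the formula yields accuracies above 100%. That requires lesions in the numerator and patients in the denominator, a mixture the text does not state. A reader might also infer bias because the clinical CEM read helps decide which sites are biopsied. The documents give no counts from which its size or direction could be judged, so that is not part of this point.

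**Conclusion.** Three conflicts stand, and all are in the written rules: the denominator of primary accuracy, a detection rate that cannot differ between modalities, and two reference rules. They should be corrected.

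It would be tempting to conclude that 83 is wrong or that the trial has only 69.3% power. The documents do not support that. Section 15.2 is a lesion-level calculation, and it reproduces at 82.95 patients and 80.0% power if the correlations combine to 0.08. The 69.3% shows only which unit fits the stated power.

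Nor is it shown that 83 is safe. It holds if 1.4 counts additional lesions only and averages in women who have none. Otherwise power is lower; the 75.6% to 57.7% above rests on assumed shares of 10% to 40%. The same gap means that no figure can be put on the detection rate from the documents.

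Confidence is high for the textual conflicts and conditional for the power figures.

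**What to change.** 1. In 15.1, define accuracy as the additional lesions whose consensus call agrees with the reference standard, divided by all additional lesions analysed. Name the extended McNemar test of 15.2 for the primary comparison. In 5.9, record BI-RADS per lesion for CEM and DBT, as for LE.
2. Define the incremental detection rate for each modality as pathology-confirmed cancers that the modality calls positive and that are absent from the outside diagnosis, divided by patients.
3. Bring 5.6, 15.1 and the Follow-up section to one primary reference rule. For example, pathology from biopsy or surgery could be primary, with follow-up used only in a sensitivity analysis.
4. In 15.2, state whether the mean of 1.4 excludes the index lesion and includes patients with no additional site. If it does both, 83 patients and 80% power stand. If not, restate the power.

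The cost is wording, one per-lesion field on two reading forms, and somewhat more reader and lesion-matching work. The form change is best made before the reads start, because 5.8 requires at least two months between reads of the same patient. The definitions need no new imaging or follow-up. Whether the patient number is affected depends on the answer to item 4.

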# 3.0 Background\*

3.1 *Current MDACC practice protocols* 

As a major tertiary cancer center, MD Anderson Cancer Center has a significant population of patients who present for staging of known breast

cancer (BC) which was already diagnosed at an outside facility (OSF), or who have OSF imaging findings that are assigned category 5 (highly suspicious with the probability of malignancy >95%) or 4C (suspicious with the probability of malignancy 50-95%) according to the American College of Radiology (ACR) Breast Imaging Reporting and Database System (BI-RADS) on OSF imaging [1]. Precise delineation of the extent of disease in the affected breast and evaluation of the contralateral breast are crucial for surgical treatment planning in BC patients [2]. Even in patients with no known BC, a second opinion at a specialized cancer center can make a significant impact on clinical management, changing the original interpretation in 36-47% of lesions [3, 4]. In patients who present with known BC at MDACC, the rate of upstaging upon second opinion interpretation and possible re-imaging is 25%, which changes surgical management in 12% of patients [5]. At the same time, the reoperation rate after breast conservation surgery in BC patients is 19% [5]. This is suboptimal and may be due to underestimation of tumor size, but this rate is lower than the national rate, which reaches 30% [2].

The current protocol for staging of OSF BC cases consists of a second read of interpretable OSF mammograms or repeating technically suboptimal mammograms, followed by ultrasound, ultrasound-guided and/or stereotactic-guided biopsies, when indicated. Some patients also require breast MRI with second look ultrasound and ultrasound- or MRIguided biopsies, which prolongs work-up and delays treatment.

At our institution, using ultrasound and MRI almost doubles the number of additional suspicious breast lesions found on mammography. 45% of these additional lesions are malignant. The sensitivities of mammography (MG), US, and MRI are 36, 71, and 85%, respectively, and their specificities are respectively 76, 68, and 39%, making MRI the most sensitive, and the MG the most specific modality. 18% of additional malignant lesions at MDA are found on MRI only [6]. Unfortunately, the need for breast MRI often delays treatment due to the limited availability of magnet time. MRI is also an expensive imaging test, further limiting access.

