# 4.0 Study Endpoints\*

4.1 Primary study endpoint:

Accuracy of CEM for incremental cancer detection in the ipsilateral and contralateral breasts. For the purpose of the study, up to 4 additional biopsy sites will be included in the analysis.

[figure not shown]
- 4.2 Secondary study endpoints:
  - Sensitivity, specificity, positive and negative predictive value of CEM, LE images, DBT, and ultrasound compared to pathology measurements as the ground truth.
  - The difference of the largest measurement of the index cancer on *LE*, *CEM*, *DBT* and *US* compared to pathology.
  - Incremental cancer detection rate provided by CEM, DBT and US.
- 4.3 Exploratory Endpoints:
  - *Rate of breast MRI utilization and the corresponding diagnosis in the study cohort.*
  - *The fraction of CEM biopsies that achieve adequate sampling of the target.*

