## 9.0 Inclusion and Exclusion Criteria\*

- 9.1 INCLUSION CRITERIA
  - Female patients 18 years of age or older with known invasive or in-situ BC diagnosed at an outside facility and presenting to MD Anderson for staging with imaging.
  - Female patients 18 years of age or older referred from outside institutions with imaging findings categorized as highly suspicious (BI-RADS 5 or 4C) on outside imaging or on rereview by MD Anderson's radiologists and referred for staging at MDACC.
  - Willingness to participate in the study and ability to provide informed consent.
- 9.2 EXCLUSION CRITERIA
  - •

•

- Breast surgery within 6 months.
- *Known allergy to iodine-containing contrast agents.*
- *History of anaphylactic reaction to any substance that required hospitalization or IV placement.*
- *Renal insufficiency; hyperthyroidism.*
- Detection of non-breast primary or metastatic cancer in the breast.

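### The cancer detection rate in section 15.1 ignores both the modality's call and what the outside facility already knew, so as written it does not deliver the incremental rate in secondary objective 3

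*Combined protocol and SAP*

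**What the plan says.** Secondary objective 3 (sections 1.0 and 2.2) is "To evaluate the incremental cancer detection rate provided by CEM, DBT, and US compared to the OSF diagnosis". Section 4.2 lists the matching endpoint as "Incremental cancer detection rate provided by CEM, DBT and US".

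The only formula is in section 15.1: "Cancer detection rate is defined as number of invasive malignancy or DCIS divided by the total sample size". The word incremental is not given a formula anywhere.

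Section 15.3 states that "Outcome variables of cancer detection rate, accuracy, sensitivity, specificity, PPV, and NPV will be estimated along with 95% confidence intervals", and that these outcomes will be "compared between the modalities using the McNemar test" or an alternative score statistic, with clustered methods to allow for several lesions per woman.

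One of the two entry groups in section 9.1 is women with "known invasive or in-situ BC diagnosed at an outside facility". The other is women with outside findings rated BI-RADS 4C or 5.

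**The concern.** The objective has three parts: a cancer must be found by a given modality, it must be new relative to the outside diagnosis, and the rate must be available for each of CEM, DBT and ultrasound. The formula has none of them. It counts cancers that exist, not cancers that a modality detected, and it does not set aside those already identified at entry.

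An analyst who applies the sentence literally reports one figure three times, with index cancers in it. An analyst who departs from it, as sections 2.2 and 15.3 suggest they should, must settle after the data are in which cancers are new, which read stands for each modality, and when an ultrasound report counts as positive. What is at stake is one secondary endpoint.

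**Working it through.** **Plan's own figures.** The plan gives no expected detection rate, so there is none to reproduce. Its one calculated figure, 83 women, was set on accuracy (section 15.2: difference 12%, discordance 20%, two-sided 0.05, 80% power, lesions per woman with mean 1.4 and variance 1, correlations 0.4 and 0.2).

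- Pairs: (1.96·√0.20 + 0.8416·√(0.20 − 0.12²))² / 0.12² = 106.6.
- Effective cluster size: (1.4² + 1)/1.4 = 2.114.
- Women: 106.6 × (1 + 1.114 × 0.08)/1.4 = 82.95, so 83.

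The 0.08 is 0.4 × 0.2, an assumption about how the two correlations combine, because the cited method paper was not available. No input is a detection rate, so the sample size does not depend on the formula at issue.

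**Step 1: the formula by modality.** Let C be all confirmed invasive cancers and DCIS. The rate is C/83 for CEM, C/83 for DBT and C/83 for ultrasound. Any difference is C/83 − C/83 = 0. In paired form, no cancer is counted for one modality and not for another, so both discordant counts b and c are 0, and the McNemar statistic (b − c)²/(b + c) is 0/0. This rests on the text alone, reading the total sample size as the same 83 women throughout.

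**Step 2: the neighbouring definitions.** In section 15.1, sensitivity and specificity count correctly diagnosed cases, and the predictive values count lesions by what the imaging predicted. Each contains the imaging result. The detection rate does not.

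**Step 3: index cancers in the numerator.** Assume one index lesion per woman.

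- All women enter with proven cancer: 1.00 per woman, 83 × 1.00 = 83.
- All women enter on BI-RADS 4C at the lowest probability in section 3.1 (50%): 0.50 per woman, 83 × 0.50 = 41.5, about 42.

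The literal rate therefore contains 0.50 to 1.00 per woman that an incremental rate should not.

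**Step 4: do modality-specific counts differ in practice?** Section 3.1 reports, for additional lesions at this institution as I read it, "45% of these additional lesions are malignant. The sensitivities of mammography (MG), US, and MRI are 36, 71, and 85%, respectively". Per 100 additional cancers, a count that requires a positive call would be 36 for mammography and 71 for ultrasound, a ratio of 71/36 = 1.97. The literal formula counts 100 for each, a ratio of 1. Section 3.1 gives no such figure for CEM or DBT, so this shows only that the missing condition can matter a great deal.

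**Step 5: what the plan already supplies.**

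| Element needed | Where it stands | Tied to this endpoint? |
|---|---|---|
| CEM read | 5.8, reading set 4 | No |
| DBT read | 5.8, only with LE (set 2) or with LE and subtraction images (set 3) | No |
| Ultrasound read | 5.3, medical records, outside the reader study | No |
| Positive call | 5.9, BI-RADS 4–5 for LE, DBT and CEM | No; none stated for ultrasound |
| Five-reader majority rule | 15.1 | No |
| Cancer not known outside | Objective 3 | Not in the formula |

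**The case against.** The strongest reply is that the sentence should not be read alone. Objective 3 names the modalities and the comparator. Section 15.3 compares the rate between modalities, which makes sense only if it is modality-specific. Section 4.1 uses incremental detection for additional sites, which points to non-index lesions. Section 5.8 identifies the complete CEM read, section 5.9 gives the positivity rule, and section 15.1 gives the majority rule.

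Most of this stands. A reader might infer that the plan has no rules from which the endpoint could be built, or that the team would really report one value for three modalities. The documents do not support either: the intent is visible and most of the parts exist. What the reply does not remove is that the one stated formula contradicts that intent, that no sentence ties the reads to this endpoint, and that ultrasound has no positivity rule.

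A reader might also infer that women, rather than cancers, should be counted. The plan does not require that. Counting cancers with the clustered methods in section 15.3 is legitimate.

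**Conclusion.** The formula is wrong as written for one secondary endpoint. Taken literally, it gives a between-modality difference of exactly 0 with no discordant pairs. That conclusion needs no assumption beyond one common denominator of 83. The index-cancer contribution of 0.50 to 1.00 per woman rests on one index lesion each, and on the 50% floor for BI-RADS 4C at the low end.

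It would be tempting to extend the criticism to the primary result. The documents do not support that: the primary accuracy comparison does not use this formula, and the 83 women were derived from accuracy inputs. The point should be fixed before analysis because a stated rule that gives the wrong quantity is more than missing detail, and correcting it is cheap.

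**What to change.** Replace the sentence in section 15.1 with:

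> For each modality, the incremental cancer detection rate is the number of pathology-confirmed additional (non-index) invasive cancers or DCIS not identified by the outside facility and called positive (BI-RADS 4–5) by that modality, divided by the number of women imaged with that modality.

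Add the following:

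- **Reads.** CEM is reading set 4 and DBT (with LE) is reading set 2, both by the five-reader majority rule. Ultrasound is the clinical report, with BI-RADS 4–5 as positive. Comparisons with ultrasound are labelled as using a clinical rather than a reader-study read.
- **Index lesion.** It is the lesion that qualified the woman for entry, whether proven cancer or BI-RADS 4C/5.
- **Earlier DBT.** Section 5.3 does not repeat DBT done within the previous 3 months. DBT already done outside is not counted as incremental to the outside diagnosis; say also that these women leave the DBT denominator, so that both counts match.
- **Comparison.** Use the clustered methods already planned in section 15.3. The proportion of women with at least one such cancer may be added.

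The cost is one replaced sentence and a few lines, with no new patients. Outside findings must be matched to lesions from the records. The DBT and CEM calls must be recorded per lesion, which section 5.9 states explicitly only for LE. The reported rates will be smaller, and comparisons with DBT may rest on fewer women.
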